8.2 Statistical Method

Simple descriptive statistics with 95% confidence interval will be performed with data collected in this study wherever applicable. All data shall be tabulated and presented in the study report. The safety and efficacy data will be analyzed using the non-parametric method wherever appropriate.

The baseline demographic characteristics within each cohort will be compared using chi-square test or exact test for categorical variables and ANOVA (analysis of variance) or Kruskal-Wallis non-parametric ANOVA test for continuous variables. The primary endpoint will be analyzed by chi-square test, while the secondary endpoints will be analyzed using the ANOVA or Kruskal-Wallis non-parametric ANOVA test for continuous endpoints and chi-square test for binary endpoints. Since this is only a small proof-of-concept study, no multiple comparisons will be made to adjust the p-values for all pairwise comparisons.

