8.1 Sample Size Determination

In part II, this is a small proof-of-concept study to evaluate low-dosed PDC-1421 arm, high-dosed PDC-1421 arm and placebo arm in the treatment of ADHD. A two stage design developed by Jung (2008) with $\alpha=0.15$ and power=80% will be used. We estimated that the PDC-1421 is considered non-effective if the response rate based on ADHD Rating Scale – Investigator Rated (ADHD-RS-IV) is 20 % or lower and is worth further study if the response rate is 40 % or higher. At the first stage, we recruit 23 subjects for each group. If the difference between the numbers of responders for any PDC-1421 arm and control arm is greater or equal to 0, we proceed to the second stage. We will recruit 10 subjects for each group at the second stage. If the difference between the accumulated numbers of responders for any PDC-1421 arm and control arm is less than 4, we reject the drug. The minimum sample size required is to recruit 69 subjects, while the maximum sample size is 99. No multiple comparison will be applied.

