5.3.4 Determination of Sample Size

A two stage design developed by Jung (2008) with significant level $\alpha = 0.15$ and power = 80%.

$$\text{Effect of PDC - 1421 : } \begin{cases} \text{Non-effective , if Response Rate } \leq 20\% \\ \text{Worth further study, if Response Rate } \geq 40\% \end{cases}$$

Stage I	Numbers of responders	Stage II
High-Dose (2 PDC-1421 Capsules) (23 subjects)	$H - P \geq 0$	Add 10 subjects and proceed to stage II
Low-Dose (1 placebo, 1 PDC-1421) (23 subjects)	$L - P \geq 0$	Add 10 subjects and proceed to stage II
Placebo (2 placebo capsules) (23 subjects)		Add 10 subjects and proceed to stage II

If the difference between the accumulated numbers of responders for any PDC-1421 arm and control arm is less than 4, we reject the drug. The minimum sample size required is to recruit 69 subjects, while the maximum sample size is 99.

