6.6 Analysis of Efficacy

6.6.1 Primary Efficacy Endpoint

An improvement of 40% or greater response rate from baseline in treatment group is considered effective and worth further study. The endpoint will be analyzed by checking if the difference of counts of responder is larger than 0 between PDC-1421 arm and placebo arm. Missing data caused by premature termination will be utilized the last observation carried forward (LOCF).

The response rate in the ADHD-RS-IV total score is defined as the following formula.

$$\text{Response rate} = \frac{\text{score}_{\text{visit}} - \text{score}_{\text{baseline}}}{\text{score}_{\text{baseline}}}$$

and the responder is defined as

$$\text{Responder : response rate} \geq 40\%$$

The descriptive statistics will include the proportion of subjects who achieved at least 40% improvement of the ADHD-RS-IV total score at Visit 6 by treatment group and placebo group. The frequency distribution of pre-treatment and post-treatment will also be tabulate and report in bar graph.

The primary measure of efficacy was the ADHD-RS-IV, consisting of 18 items designed to reflect current symptomatology of ADHD based on DSM-IV-TR criteria. Each item is scored on a 4-point scale ranging from 0 (reflecting no symptoms) to 3 (reflecting sever symptoms) with total scores ranging from 0 to 54, which is calculated by summing up scores of subscales. The 18 items may be grouped into 2 subscales:

- For inattention (IA) subscale raw score: Add the odd-numbered 9 items. Higher score indicate severe inattention symptoms.
- For hyperactivity-impulsivity (HI) subscale raw score: Add the even-numbered 9 items. Higher score indicate severe hyperactivity-impulsivity symptoms.
- To obtain the total raw score: Add the IA and HI subscale raw scores.

Following SAS procedures will be applied for chi-Square test between arms.

```
%macro;  
proc freq data = ____;  
    table response*treatment/chisq;  
    output out = chiqtest chisq;  
run;  
%mend;
```

When there has a missing value issue, the following LOCF SAS procedures will be applied.

```
%macro;  
DTAT locf1;  
    LENGTH dtype $15;  
    RETAIN retain;  
    SET lab;  
    BY usubjid visit;  
  
    IF FIRST . visit ^=0 THEN retain = . ;  
    IF qsstresc NE . THEN retain = qsstresc;  
    IF qsstresc= . THEN DO;  
        qsstresclocf = retain;  
        dtype = 'LOCF';  
    END;  
    ELSE qsstresclocf = qsstresc;  
RUN;  
%mend;
```

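### The 80% power belongs to the two-stage responder-count rule, but the chi-square test named as primary analysis is a different test, with about 64% power (one dose v placebo) if run two-sided at 0.15

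*Protocol*

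**What the plan says.** Protocol 8.1: "A two stage design developed by Jung (2008) with $\alpha=0.15$ and power=80% will be used". The drug counts as non-effective if the response rate "is 20 % or lower and is worth further study if the response rate is 40 % or higher". Stage I takes 23 patients per arm, with this condition on the responder difference: "any PDC-1421 arm and control arm is greater or equal to 0, we proceed to the second stage". Stage II adds 10 per arm, which makes 33 per arm. The final rule appears in Protocol 8.1 and again in SAP 5.3.4: "If the difference between the accumulated numbers of responders for any PDC-1421 arm and control arm is less than 4, we reject the drug".

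Protocol 8.2, and the synopsis in the same terms: "The primary endpoint will be analyzed by chi-square test". No significance level, direction or choice of arms is given, and the count rule is not mentioned.

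SAP 6.6.1 contains both approaches. It describes a check that the responder difference exceeds 0, and it supplies SAS code with the line "table response*treatment/chisq", in which the input dataset is left blank. SAP 5.4 records that the interim requirement was not met, that the study was terminated, and that the chi-square test between arms will not be carried out.

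**The concern.** Power and type I error belong to a particular test. Sections 8.1 and 8.2 name different procedures for the same endpoint, and only the first was sized. The count rule looks in one direction only, PDC-1421 above placebo. A standard chi-square statistic has no direction, and if all three arms enter the table it also spends a second degree of freedom on differences that are not the planned contrast.

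Two things are at stake. A reader of 8.1 and 8.2 together would attach 80% power to a test that does not have it. And the two procedures can disagree on the same data, so that a dose clears the cut-off of 4 while the p-value reported for the primary endpoint is not significant.

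**Working it through.** **Inputs.** From Protocol 8.1: 23 then 10 per arm (33 in total), continue if the difference is ≥ 0, reject the drug if the cumulative difference is < 4, alpha 0.15, power 80%, rates 20% and 40%. Assumptions: the placebo rate is 20% (not stated separately), and the low-dose rate is 20%, 30% or 40% in the three-arm scenarios. The chi-square is evaluated at 0.15 (the design alpha) and at 0.05 (a level suggested only by the 95% confidence intervals).

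**1. Reproduce the plan's figure.** Let D1 be the difference in responders (one dose minus placebo) at 23 per arm and D2 the difference among the next 10 per arm. The probability of passing is P(D1 ≥ 0 and D1 + D2 ≥ 4), by exact binomial enumeration.
- 20% v 20%: 0.139
- 20% v 40%: 0.801

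So alpha 0.15 and power 80% reproduce as a directional rule for one dose against placebo. The type I error depends on the common rate: 0.171 at 30% and 0.187 at 40%.

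**2. Pairwise chi-square, 33 per arm, 20% v 40%.** The statistic is z² with z = (x₁ − x₀)/33 ÷ √(p̄(1 − p̄)·2/33), where p̄ = (x₁ + x₀)/66.

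Normal approximation: the null SE is √(2 × 0.3 × 0.7/33) = 0.1128 and the alternative SE is √((0.16 + 0.24)/33) = 0.1101.
- Two-sided 0.15: Φ((0.2 − 1.440 × 0.1128)/0.1101) = Φ(0.34) = 0.634
- Two-sided 0.05: Φ((0.2 − 1.960 × 0.1128)/0.1101) = Φ(−0.19) = 0.424

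Exact enumeration gives 0.639 and 0.440, or 0.52 and 0.32 with continuity correction. Adding the stage I stop changes the uncorrected figures by less than half a point.

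**3. Three-arm 2-df chi-square, 33 per arm, exact.**

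| Placebo / low / high | Power at 0.15 | Power at 0.05 |
|---|---|---|
| 20 / 20 / 40% | 0.659 | 0.458 |
| 20 / 30 / 40% | 0.550 | 0.338 |
| 20 / 40 / 40% | 0.643 | 0.426 |

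**4. Where the pairwise loss comes from.** A directional chi-square at one-sided 0.15 (two-sided p < 0.30 in favour of PDC-1421) has power 0.792, or 0.789 with the stage I stop, and null rejection 0.151 at a 20% common rate with that stop. At 0.15, the fall from 0.801 to 0.639 is 16.2 points. Of this, 0.792 − 0.639 = 15.3 points come from making the test two-sided, which leaves only about 0.078 of its error in the favourable direction. The other 0.9 point comes from using the chi-square instead of the count cut-off.

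**5. Do the two procedures disagree?** Take a difference of exactly 4, say 11 v 7 responders: p̄ = 18/66 = 0.273, z = 0.1212/0.1096 = 1.106, two-sided p = 0.269. Other pairs: 7 v 3 gives 0.170, 9 v 5 gives 0.228, 14 v 10 gives 0.306, 17 v 13 gives 0.323. With 0 to 2 placebo responders p is lower (0.04 to 0.13), but so few responders has a probability of about 3% at a 20% placebo rate.

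At 20% v 40% with 33 per arm and no interim stop, P(difference ≥ 4) = 0.804. The share of those outcomes with two-sided p ≥ 0.05 is 1 − 0.440/0.804 = 45%, and with p ≥ 0.15 it is about 1 − 0.639/0.804 = 21%.

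**The case against.** The strongest reply is that the plan never claims 80% power for the chi-square. Protocol 8.1 attributes it to the Jung design, and both documents tie rejection of the drug to responder counts. No decision hangs on the chi-square. That stands. A reader might infer that the trial is underpowered for its go/no-go decision, or that no rule governs that decision. The documents support neither: the count rule is pre-specified and has the stated power for each dose.

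The size of the gap also depends on choices the documents leave open. The 0.05 level is not set for this test. Sidedness is not stated. It is tempting to say that the SAP code specifies a three-arm 2-df test, but its dataset is blank, Protocol 8.2 speaks of pairwise comparisons, and SAP 5.4 speaks of tests between arms. The three-arm figures are therefore scenarios.

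Finally, SAP 5.4 drops the test and the trial stopped after the interim, so under the current SAP the conflict in step 5 cannot arise in the reported results. This limits the practical consequence. It does not repair the wording: the reason given is termination, not the mismatch, and Protocol 8.2, the synopsis and the code in SAP 6.6.1 still present the chi-square as the analysis of the primary endpoint.

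**Conclusion.** The point holds as a mismatch between the sized rule and the named primary test. At 33 per arm, with placebo at 20% and the active dose at 40%, the count rule has 80.1% power. The named test, if undirected, has 64% (0.15) or 44% (0.05) for one dose against placebo, and 55–66% or 34–46% in a three-arm table with the low dose at 20–40%. Choosing a chi-square is not in itself the problem, since a directional per-dose version at one-sided 0.15 has about 79%. The defect is that level, direction and contrast are missing, as is any statement of how the test relates to the count rule. Because the SAP no longer runs the test, this is a correction to the plan's wording. It is not evidence that a reported result is wrong.

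**What to change.** In Protocol 8.2, the synopsis and SAP 6.6.1, name the 8.1 count rule as the primary analysis that decides go/no-go: each dose against placebo, cumulative difference of at least 4 at 33 per arm, after the stage I condition. The over-0 check in SAP 6.6.1 matches neither cut-off in 8.1 (at least 0, then at least 4) and should be brought into line in the same edit. State that the 80% power applies only to the count rule, and that its per-dose type I error is 0.139 at a common rate of 20%, rising to about 0.17–0.19 at 30–40%.

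Label any chi-square as supportive. If one is kept for inference, specify it per dose against placebo, directional, at one-sided 0.15, and give its power as about 79%.

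The cost is wording only. No extra patients are needed, and no SAS work while SAP 5.4 stands. The downside is that the lenient one-sided 0.15 standard becomes explicit, as does the fact that the rule's error exceeds 0.15 at higher common response rates.

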3.3 Secondary Endpoint

Table 12. The secondary efficacy endpoints in part II

Number	Items
1	Symptom remission in ADHD Rating Scale-Investigator Rated (ADHD-RS-IV total score ≤ 18) up to 8 weeks treatment.
2	Change from baseline in the ADHD Rating Scale-Investigator Rated (ADHD-RS-IV), Conners' Adult Attention-Deficit/Hyperactivity Disorder Rating Scale-Self Report: Short Version (CAARS-S:S) and Empirical-Sluggish Cognitive Tempo (E-SCT) score up to 8 weeks treatment.
3	Clinical Global Impression - improvement (CGI -I) score of 2 or lower up to 8 weeks treatment.

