4.1 Inclusion Criteria

1. Aged 18-70 years
2. Female subjects of child-bearing potential must test negative to pregnancy and use appropriate birth control method from the beginning of study to the 15 days later after ending of study
3. Subjects must be able to understand and willing to sign informed consent
4. Able to discontinue the use of any psychotropic medications for the treatment of ADHD symptoms at screening
5. Meet strict operational criteria for adult ADHD according to the Diagnostic and Statistical Manual of Mental Disorders, 5th Edition (DSM-5)
6. A total score of 28 or higher of ADHD Rating Scale-Investigator Rated (ADHD-RS-IV) at screening
7. Have a moderate or severe symptom of ADHD with score of 4 or higher in Clinical Global Impression- Severity (CGI-S) at screening

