6.2 Methods and Timing for Assessing, Recording, and

Analyzing of Efficacy Parameters.

The data obtained from eligible subjects before study drug administration in Visit 2 or Visit 1 (if no data at Visit 2) are set as baseline. After the beginning of treatment, the collection of data of efficacy parameters are performed at planned treatment schedule as [section 5.2](#). CRC shall record these data in CRF in detail after each visit during the treatment period. In part II, data comparison between group of 1 capsule TID, 2 capsules TID of PDC-1421 Capsule and 2 capsules TID of placebo will be conducted in final report of this study to evaluate which group(s) of PDC-1421 Capsule are efficient. The rating scales are as follows:

- **ADHD-RS-IV**

The ADHD-RS-IV with Adult Prompts is an 18-item scale base on the DSM-IV-TR' criteria for ADHD that provides a rating of the severity of symptoms¹⁵. The adult prompts serve a guide to explore more fully the extent and severity of ADHD symptoms and create a framework to ascertain impairment. The odd-numbered 9 items assess inattentive symptoms and the even-numbered 9 items assess hyperactive-impulsive symptoms. Scoring is based on a 4-point, yielding a possible total score of 0 – 54. Likert-type severity scale: 0 = Never or Rarely, 1 = Sometimes, 2 = Often, 3 = Very Often. Clinicians should score the highest score that is generated for the

prompts for each item.

For inattention (IA) subscale raw score: Add the odd-numbered 9 items

For hyperactivity-impulsivity (HI) subscale raw score: Add the even-numbered 9 items

To obtain the total raw score: Add the IA and HI subscale raw scores.

- **Clinical Global Impression¹⁶**

At the baseline visit, clinicians completed the CGI-S and were asked to evaluate the severity of subjects' illness with respect to ADHD symptoms based on the clinician's experience with this particular population. Possible scores ranged from 1 (normal, not at all ill) to 7 (among the most extremely ill). At all subsequent study visits, clinicians used the CGI-I to rate the subjects' total improvement based on comparison with their baseline assessment from 1 (very much improved) to 7 (very much worse).

- **CAARS-S:S**

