6.6.2 Secondary Efficacy Endpoints

- **ADHD-RS-IV**

The scores of ADHD-RS-IV will be assessed by the descriptive statistics.

- **CGI**

The scores of 2 or lower of CGI will be summarized by way of frequency and percentage.

At the screen and baseline visit, clinicians completed the CGI-S and were asked to evaluate the severity of subjects' illness with respect to ADHD symptoms based on the clinician's experience with this particular population. Possible scores ranged from 1 (normal, not ill at all) to 7 (among the most extremely ill subjects). At all subsequent study visits, clinicians used the CGI-I to rate the subjects' total improvement based on comparison with their baseline assessment from 1 (very much improved) to 7 (very much worse).

- **CAARS-S:S**

The T-scores of CAARS-S:S (Conners et al. 1999) will be assessed for each visit change from baseline by the descriptive statistics

Conners' Adult Attention-Deficit/Hyperactivity Disorder Rating Scale-Self Report: Short Version (Conners et al., 1998; CAARS-S:S) consists of 26 items rated from 0 'not at all, never' to 3 'very much, very frequently.' Four subscales each composed of 5 items (A: Inattention/Memory Problems; B:

Hyperactivity/Restlessness; C: Impulsivity/Emotional Lability; and D: Problems with Self-Concept) as well as a 12-item ADHD index can be computed. The raw scores were converted into standard T-scores by Microsoft Excel program which designed according to the Profile form of CAARS QuikScore forms. A T-score is a standard score with a mean of 50 and a standard deviation of 10 in all samples and across all scales. As a general guide, T-scores can be interpreted using the guidelines provided in the table below. The CAARS-S:S was self-assessed by the subjects from Visit 1 to Visit 7.

Interpretive Guidelines for T-Scores and Percentiles

T-Score Range	Percentile Range	Guideline
Above 70	98+	Very much above average
66 to 70	94 - 98	Much above average
61 to 65	86 - 94	Above average
56 to 60	74 - 85	Slightly above average
45 to 55	27 - 73	Average
40 to 44	16 - 26	Slightly below average
35 to 39	6 - 15	Below average
30 to 34	2 - 5	Much below average
Below 30	< 2	Very much below average

Reference: CAARS Adult ADHD Rating Scales Technical Manual

• E-SCT

The scores of E-SCT will be assessed for each visit change from baseline by the descriptive statistics

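### Change-from-baseline scales are compared without adjusting for the baseline score; ANCOVA would be more precise, though the documents do not fix by how much

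*Protocol*

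**What the plan says.** Protocol 3.3 (Table 12) lists "Change from baseline in the ADHD Rating Scale-Investigator Rated (ADHD-RS-IV"), together with change in CAARS-S:S and E-SCT, as a secondary endpoint over the 8 weeks of treatment. Protocol 8.2 says that "the secondary endpoints will be analyzed using the ANOVA or Kruskal-Wallis non-parametric ANOVA test for continuous endpoints". It adds that pairwise p-values will not be adjusted for multiplicity and that 95% confidence intervals accompany the descriptive statistics where applicable.

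Baseline is defined in Protocol 6.2 as "data obtained from eligible subjects before study drug administration in Visit 2 or Visit 1 (if no data at Visit 2"). The schedule in Protocol 5.2 (Table 15) has all three scales at both visits, so a baseline is planned for every subject. Neither document mentions ANCOVA, a baseline covariate or a mixed model for these scales.

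The SAP takes a different course. Section 6.6.2 states "The scores of ADHD-RS-IV will be assessed by the descriptive statistics", and treats change in CAARS-S:S and E-SCT in the same way. Section 5.4 says the study was terminated because the interim results did not meet the protocol's requirement, and that the between-arm chi-square and Wilcoxon signed-rank tests will not be done. It does not mention ANOVA or Kruskal-Wallis, and it also says that analysis follows the protocol. Section 6.2 still asks for a mean with 95% CI for continuous variables.

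**The concern.** A change score subtracts the whole baseline value, whatever the correlation between baseline and outcome. Unless that correlation happens to equal the ratio of the baseline SD to the week-8 SD, the change score stays correlated with baseline. Chance differences in baseline between arms then enter the between-arm contrast as noise. ANCOVA on the scale's own baseline removes that noise.

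The arms are small: "At the first stage, we recruit 23 subjects for each group", and 33 per group if the second stage runs. The standard error of a baseline difference between two arms is √(2/23) ≈ 0.29 SD at 23 per arm and √(2/33) ≈ 0.25 SD at 33. With equal SDs a change score carries (1 − ρ) of that difference, so at an assumed ρ of 0.5 about 0.15 SD of avoidable noise remains with 23 per arm. This is the precision loss seen from another side, not a second defect.

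What is at stake is the clarity of the dose-versus-placebo estimates on the continuous scales. Protocol 6.2 wants to know which dose groups are effective. An overall three-group p-value does not answer that, and no dose-minus-placebo difference with a confidence interval is specified for any scale.

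**Working it through.** **The plan's own figure.** The only design calculation is for the binary primary endpoint: "A two stage design developed by Jung (2008) with $\alpha=0.15$ and power=80% will be used". An exact calculation for one active arm against placebo (continue if the responder difference is at least 0 with 23 per arm, accept if it is at least 4 with 33 per arm) gives type I error 0.139 at 20% versus 20% and power 0.801 at 40% versus 20%. The stated design reproduces. It says nothing about the continuous scales, for which the documents give no SD, correlation or effect size.

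**Inputs for the continuous scales.**
- ρ, the correlation between baseline and week 8: not in the documents; assumed 0.3 to 0.6.
- k = baseline SD / week-8 SD: not in the documents; assumed 1.0, 0.8 and 0.7. A value below 1 is plausible for ADHD-RS-IV because entry requires "A total score of 28 or higher of ADHD Rating Scale-Investigator Rated (ADHD-RS-IV) at screening" on a 0–54 scale, which can narrow the baseline spread while week-8 scores range freely. CAARS-S:S and E-SCT have no entry floor.
- Total N: 69 after stage I, 99 after stage II (Protocol 8.1).

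**Formulas**, with the week-8 SD set to 1:
- Variance of change: 1 + k² − 2ρk.
- Residual variance under ANCOVA: 1 − ρ².
- The difference between them is (k − ρ)², so the proportional reduction is (k − ρ)² / (1 + k² − 2ρk).
- With k = 1 this is (1 − ρ)/2.
- The reduction is never negative in large samples, and is zero when k = ρ.

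**Examples.**
- k = 1, ρ = 0.3: variances 1.40 and 0.91, ratio 0.65, reduction 35%. CI width falls by 1 − √0.65 = 19%.
- k = 1, ρ = 0.6: 0.80 and 0.64, ratio 0.80, reduction 20%. CI width falls by 11%.
- k = 0.8, ρ = 0.3: 1.16 and 0.91, reduction 21.6%.
- k = 0.7, ρ = 0.6: 0.65 and 0.64, reduction 1.5%.

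**Variance reduction (CI narrowing in brackets), before the cost of the extra parameter:**

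| k | ρ = 0.3 | ρ = 0.4 | ρ = 0.5 | ρ = 0.6 |
|---|---|---|---|---|
| 1.0 | 35.0% (19.4%) | 30.0% (16.3%) | 25.0% (13.4%) | 20.0% (10.6%) |
| 0.8 | 21.6% (11.4%) | 16.0% (8.3%) | 10.7% (5.5%) | 5.9% (3.0%) |
| 0.7 | 15.0% (7.8%) | 9.7% (5.0%) | 5.1% (2.6%) | 1.5% (0.8%) |

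Over a wider grid (ρ 0.3 to 0.8, k 0.6 to 1.0) the reduction runs from 0% to 35%.

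**Cost of the covariate.** Estimating one slope inflates the variance by about 1/(N − 5): 1/64 = 1.6% at N = 69 and 1/94 = 1.1% at N = 99. At N = 69 this cancels the gain in the least favourable cell of the table and takes about one percentage point off the most favourable.

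All of this compares ANCOVA with ANOVA on change. It does not apply to Kruskal-Wallis.

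**The case against.** The strongest objection is that the SAP no longer plans the criticised analysis. It makes the scales descriptive and drops between-arm tests after termination. This largely stands: a reader might infer that the final report will rest on an unadjusted test, and the SAP does not say so. It does not settle the matter, however. SAP 5.4 leaves ANOVA and Kruskal-Wallis unmentioned while deferring to the protocol, and one of the two tests it drops, the Wilcoxon signed-rank, is not among those Protocol 8.2 names. SAP 6.2 also keeps means with 95% CIs, which readers will compare between arms.

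The second objection is that the go/no-go rule uses responder counts only, so these scales drive no formal decision. That stands and limits the consequence.

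Third, a reader might infer that the plan offers no dose-versus-placebo comparison at all. Protocol 8.2 refers to pairwise p-values and to 95% CIs where applicable. The fair criticism is narrower: no interval for the dose-minus-placebo difference is specified.

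Fourth, a reader might want country in the model because the trial runs in the US and Taiwan. Protocol 3.4 describes no stratification by country or site, and nothing in the calculation depends on such a term.

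**Conclusion.** The omission is certain: Protocol 8.2 compares change scores without the baseline value that the trial collects. The comparison remains unbiased under randomisation; what it gives up is precision.

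The size is conditional. Against ANOVA on change, the variance reduction is 20% to 35% if ρ is 0.6 to 0.3 and the SDs are equal. It is about 1.5% to 22% over the same ρ if the baseline SD is 0.7 to 0.8 of the week-8 SD. A reader might take 20% to 35% as a known loss in this trial. The documents do not support that: they contain neither ρ nor any SD, and equal SDs are doubtful for ADHD-RS-IV because of the entry floor. Nor does the figure translate directly into interval width, which falls by only about 11% to 19% even in the favourable case.

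Adjustment is worth making because it costs almost nothing. Its practical effect is now on estimates that are still to be reported, since the SAP plans no formal between-arm test of these scales.

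**What to change.** In Protocol 8.2, analyse Visit 6 change in each scale by ANCOVA with treatment and that scale's own baseline score. Report each dose-minus-placebo adjusted mean difference with its 95% CI. Keep Kruskal-Wallis, or a rank ANCOVA, as a sensitivity check for non-normal scores. Leave out a country term.

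In SAP 6.6.2, add the same adjusted differences and intervals. Present them as estimation and label them post hoc, because the SAP (April 2024) was finalised after the interim result was known. In SAP 5.4, state whether the protocol's ANOVA or Kruskal-Wallis comparisons are still to be run.

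The cost is one extra model per scale and a few lines of text, with no new data. If baseline adjustment adds nothing (k = ρ), the loss is about 1% to 2% of precision through the extra parameter.
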